#### 14.1.1. AE REPORTING

All AEs will be evaluated to determine whether the event further meets the criteria for ADE, SAE, MAE, SADE, or UADE and will be subject to the respective reporting requirements as outlined in the sections below. Non-serious and non-device related AEs must be reported to the Sponsor in a timely manner and must also be submitted to the IRB/EC per policy.

#### 14.2. ADVERSE DEVICE EFFECTS (ADE)

An adverse device effect is defined as any untoward adverse event related to the use of an investigational or unintended response to a medical device.

Note 1: This definition includes adverse events resulting from insufficient or inadequate Instructions for Use, deployment, implantation, installation, or operation, or any malfunction of the investigational medical device. This definition includes any event resulting from insufficiencies or inadequacies in the Instructions for Use or the deployment of the device or any event that is a result of user error (See **Section 15**).

Note 2: This definition includes any event resulting from use error or from intentional misuse of the investigational medical device (See **Section 15**).

A list of events that may be associated with the study device and/or the index procedure is provided in **Section 13.1**.

#### 14.2.1. ADE REPORTING

All ADEs must be evaluated to determine whether the event further meets criteria for an SADE (See **Section 14.5**) and would be subject to respective reporting requirements. Non-serious, anticipated ADEs must be reported by the Investigator (or designee) to the Sponsor in a timely manner and must also be submitted to the IRB/EC per policy. If the event occurred as a result of a device event, respective reporting requirements must be followed as outlined in **Section 15**.

#### 14.3. SERIOUS ADVERSE EVENTS (SAE)

A serious adverse event (SAE) is defined an adverse event that:

- led to death,
- led to a serious deterioration in the health of the subject, that either resulted in:
- a life-threatening illness or injury, or
- resulted in a permanent impairment of a body structure or a body function, or

- required in-patient hospitalization or prolongation of existing hospitalization, or
- resulted in medical or surgical intervention to prevent life-threatening illness or injury or permanent impairment to body structure or a body function, or,
- led to fetal distress, fetal death or a congenital abnormality or birth defect.

Note: Planned hospitalization for a pre-existing condition, or a procedure required by the investigational plan without serious deterioration in health, is not considered a serious adverse event.

#### 14.3.1. SAE REPORTING

All SAEs must be evaluated to determine whether the event further meets criteria for an SADE (See **Section 14.5**) and would be subject to respective reporting requirements. All events that meet the criteria above for SAEs must be reported by the Investigator (or designee) to the Sponsor **within 2 business days from first knowledge of event** and must also be reported to the IRB/EC per policy.

#### 14.4. MAJOR ADVERSE EVENTS (MAE)

For the purpose of this study, the definition of major adverse event(s)(MAEs) includes the following events that comprise safety and observational endpoints for this study:

- Index limb amputation (major)
- Clinically-driven target lesion revascularization (TLR)
- All-cause death

#### 14.4.1. MAE REPORTING

All events that meet the criteria above for an MAE must be reported by the Investigator (or designee) to the Sponsor **within 2 business days from first knowledge of the event**, and must also be reported to the IRB/EC per policy.

#### 14.5. SERIOUS ADVERSE DEVICE EFFECTS (SADE)

A serious adverse device effect (SADE) is defined as an adverse device effect (ADE) that results in any of the consequences characteristics of a serious adverse event (SAE).

#### 14.5.1. SADE REPORTING

All events that meet the criteria above for an SADE must be reported by the Investigator (or designee) to the Sponsor **within 2 business days from first knowledge of event** and must also be reported to the IRB/EC per policy. If the event occurred as a result of a device event, respective reporting requirements must be followed as outlined in **Section 15**.

#### 14.6. UNANTICIPATED ADVERSE DEVICE EFFECTS (UADE)

An Unanticipated Adverse Device Effect (UADE) is any serious adverse effect on health or safety or any life-threatening problem or death caused by, or associated with, a device, if that effect, problem, or death was not previously identified in nature, severity, or degree of incidence in the investigational plan; or any other unanticipated problem associated with a device that relates to the rights, safety, or welfare of the subjects.

#### 14.6.1. UADE REPORTING

Any event that is suspected of meeting UADE criteria should be reported in the same manner as an SAE or SADE and must be reported by the Investigator (or designee) to the Sponsor **within 2 business days from first knowledge of event** and must also be reported to the IRB/EC per policy. All SAEs will be reviewed by the Sponsor (or designee) to determine if UADE criteria is met, and if so will immediately conduct an evaluation and report the results of the evaluation to FDA, all reviewing IRBs/ECs, and participating investigators within 10 business days after the Sponsor first receives notice of the effect.

### 15. STUDY DEVICE EVENT REPORTING

A Study Device Event refers to the performance of the study device and the occurrence of a deficiency or malfunction as defined in sub-sections below. Device events are to be reported on the Device Event eCRF and submitted to the sponsor as soon as possible and **within 2 business days of first knowledge of occurrence**. Any adverse event suspected of resulting from a device event must be reported per the required timelines as outlined in **Section 14**.

#### 15.1. DEVICE DEFICIENCY

Inadequacy of a medical device related to its identity, quality, durability, reliability, safety or performance, such as malfunction, misuse or user error, and inadequate labeling.

#### 15.2. DEVICE MALFUNCTION

A malfunction is defined as a failure of a device to meet its performance specifications or otherwise to perform as intended.

### 16. STATISTICAL CONSIDERATIONS

#### 16.1. INTRODUCTION

Descriptive statistics for each variable will be calculated which will include the number of observations, mean, standard deviation, median, minimum and maximum for continuous variables and will include the number and percent of observations for categorical variables.

When the mean is found not to be an appropriate measure of central tendency, alternative statistics will be considered (e.g. median). When the distribution of a variable does not support the use of parametric statistics, nonparametric approaches or data transformations may be implemented. If data transformations are used they will be specified in the final clinical report.

#### 16.2. ANALYSIS GROUPS

***Intent to Treat (ITT)***: A subject is defined as an intent-to-treat (ITT) patient once the subject has met all the inclusion and exclusion criteria including angiographic criteria and the Tack Endovascular System is advanced through the introducer sheath. See **Section 10.2.1 – 10.3.1** for details.

***Per Protocol (PP)***: The per-protocol (PP) population is defined as the subset of the ITT population with evaluable data that have met the definition for Device Success, excluding subjects with major protocol deviations such as:

- A major inclusion/exclusion criterion violation; or
- A major procedural deviation

The criteria for deviations meeting the classification of “major” will be defined before study endpoint data is available for statistical analysis. All major deviations will be adjudicated by an independent designee without visibility to study results.

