#### 10.3.1. ENROLLMENT (INTENT-TO-TREAT)

A subject is defined as an intent-to-treat (ITT) patient and officially enrolled in the study once the Tack Endovascular System is advanced through the introducer sheath. Subjects in whom at least one Tack is not placed, will be exited after 12 months. Subjects in whom at least one Tack is placed will be followed for 36 months.

In addition, the per-protocol (PP) population will be defined as ITT subjects with evaluable data that have met the definition for device success, excluding subjects with major deviations such as:

- A major inclusion/exclusion criterion deviation; or
- A major procedural deviation

The criteria for deviations meeting the classification of “major” will be defined before study endpoint data is available for statistical analysis. All major deviations will be adjudicated by an independent designee without visibility to study results.

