### 16.3. ENROLLMENT SAMPLE SIZE

The maximum sample size required for the primary objectives is 178 subjects meeting the ITT definition for primary efficacy that are evaluable for the primary patency endpoint measured at 12 months. The sample size was increased for 15% attrition over 12 months, resulting in 210 enrolled subjects. See Sample Size Rationale in **Section 16.7** and **Section 16.8** for sample size calculations specific to each primary endpoint.

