### 16.4. ADMINISTRATIVE REPORTS

The study will permit the use of either drug-coated or standard balloons in the angioplasty procedure that immediately precedes Tack placement. The performance goal for the primary efficacy objective depends on the proportion of subjects enrolled, i.e. ITT patients who were treated with standard or drug-coated balloons. Once the index procedure is completed for all enrolled subjects, the proportion of subjects treated with standard balloons and drug-coated balloons will be calculated. The proportions are the weights in the formula to calculate the performance goal. The calculation is described in **Section 16.8 Performance Goal**. The performance goal for primary efficacy will be fixed in advance of or prospectively to the primary efficacy analysis. There is no Type I error adjustment for this report given that no hypotheses will be tested.

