### 16.6. HANDLING OF MISSING DATA

The primary statistical analysis will be conducted using the observed data with standard imputations used when the 12 month DUS determination is missing but an earlier or later DUS

or angiogram are available in the ITT sample (see Primary Statistical Analysis in **Section 16.8** for more detail).

Additionally, a sensitivity analysis to the missing data in the intent-to-treat sample will be conducted. The sensitivity analysis will include a best case, worst case and tipping point analysis. The best case analysis will impute successes for the missing data. The worst case analysis will impute failures for missing data. The tipping point analysis starts with the best case analysis and continues until the worst case analysis is completed, by increasing the number of missing cases imputed as failures by one in each analysis. The goal of the tipping point analysis is to determine at what point the imputation of failures causes the statistical evaluation of the endpoint to lose statistical significance. If the worst case analysis maintains statistical significance, the tipping point analysis is not necessary.

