#### 16.8. PRIMARY SAFETY OBJECTIVE

Subjects Included the Analysis: Subjects who meet the ITT definition as specified in **Section 16.2 and 10.3.1**.

Endpoint: Freedom from the occurrence of any new-onset major adverse event(s) (MAEs) defined as index limb amputation (above the ankle), CEC adjudicated clinically-driven target lesion revascularization (CD-TLR), or all-cause death at 30 days as specified in **Section 6.1**.

Hypothesis and Performance Goal: The VIVA performance goal of 88% will be used as the performance goal for this endpoint.

H0: Freedom from MAE (pMAE) is less than or equal to 88% at 30 days, pMAE ≤ 88%

H1: Freedom from MAE is greater than 88% at 30 days, pMAE > 88%

Sample Size Rationale: Using PASS 2012, a one-sample Exact Test, power = 90%, one-sided Type I error controlled at 5.0%, a performance goal of 88% and an assumed freedom from MAE at 30 days in Group 1 of 95%, 138 subjects with 30 days of follow-up and/or an MAE prior to 30 days are required for the analysis.

---

**Primary Statistical Analysis:** The primary statistical analysis will be conducted in subjects who meet the ITT definition and have observed data for the primary safety endpoint. The primary statistical method is a one-sample exact test comparing the proportion of subjects free from a MAE to the performance goal using a one-sided  $\alpha = 0.05$ . The exact one-sided 95% confidence interval for the proportion of subjects free from MAE will be calculated.

The freedom from MAE proportion will be calculated such that the numerator is the number of subjects in whom a MAE did not occur within 30 days of the index procedure. The denominator is the number of subjects with 30 days of follow-up plus the number of subjects with an MAE prior to 30 days who exited the study early, if any.

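### Section 16.2 adds an eligibility condition to ITT that Sections 10.3.1 and 19 lack, so the two definitions cited for both primary analyses disagree on treated subjects found ineligible

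*Combined protocol and SAP*

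**What the plan says.** The plan defines ITT in three places.

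- **Section 10.3.1:** a subject is ITT and "officially enrolled in the study once the Tack Endovascular System is advanced through the introducer sheath". There is no eligibility condition.
- **Section 19 (Study Definitions):** the same rule as 10.3.1.
- **Section 16.2:** a subject is ITT "once the subject has met all the inclusion and exclusion criteria including angiographic criteria", and the system has been advanced through the sheath.

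Both primary analyses draw on two of these at once. Section 16.8 takes "Subjects who meet the ITT definition as specified in" Sections 16.2 and 10.3.1, and Section 16.9 does the same.

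Three further provisions bear on the reading:

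- The per-protocol set in 16.2 is a subset of ITT, and one ground for leaving it is "A major inclusion/exclusion criterion violation". Major deviations are to be "adjudicated by an independent designee without visibility to study results".
- Section 16.4 sets the efficacy performance goal from "the proportion of subjects enrolled, i.e. ITT patients who were treated with standard or drug-coated balloons", which treats enrolled and ITT as the same group.
- In Section 16.6, "a sensitivity analysis to the missing data in the intent-to-treat sample will be conducted".

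**The concern.** The definitions coincide for every eligible subject and part company only on a subject who was treated and did not meet the criteria. Under 10.3.1 and Section 19 that subject is in both primary analyses. Under the literal wording of 16.2 the subject is in neither.

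Both primary endpoints are one-sample tests against a performance goal, so the result depends directly on who is in the denominator. A subject left out under 16.2 cannot return through any planned analysis of the primary endpoints: the per-protocol set is a subset of ITT, and the best-case, worst-case and tipping-point analyses run inside ITT. The results-blind adjudication is written for the per-protocol deviations, and nothing comparable is written for ITT membership. With two definitions cited together, the choice between them could be made after outcomes are known.

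**Working it through.** **1. The definitions side by side**

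| Section | Eligibility required for ITT? | Treated subject found ineligible |
|---|---|---|
| 10.3.1 | No | In ITT |
| 19 | No | In ITT |
| 16.4 | Enrolled equated with ITT | In ITT |
| 16.2, ITT paragraph | Yes | Not in ITT |
| 16.2, PP paragraph | Removes major eligibility violators from ITT | Presupposed to be in ITT |

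Section 16.2 is therefore at odds with itself as well as with 10.3.1. If ITT already required every criterion to be met, the per-protocol eligibility exclusion would have nothing to remove.

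**2. Reproducing the plan's figures**

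Method: exact one-sided binomial test. The success threshold r is the smallest value with P(X ≥ r | n, goal) ≤ alpha; power is P(X ≥ r | n, assumed rate).

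- Efficacy (16.9): n=178, goal 53%, assumed 65%, alpha 0.025. Threshold 108, actual alpha 0.0237, power 90.0%, as stated.
- Enrolment (16.3): 178/(1 − 0.15) = 209.4, rounded up to 210, as stated.
- Safety (16.8): n=138, goal 88%, assumed 95%, alpha 0.05. Threshold 128, actual alpha 0.0493, power 91.4%, consistent with the stated 90%.

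**3. How often the case might arise**

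The documents give no expected number of ineligible treated subjects. The nearest figure is Table 2 in Section 4.1: in the earlier TOBA study the core lab saw no dissection in 3 of 127, against 1 of 128 by site report. In TOBA II, absence of dissection is an angiographic exclusion (7.5.4, item 5), and 18.9 has the core labs read images against the eligibility criteria. As an assumption only, 3/127 = 2.36%, and 0.0236 × 210 ≈ 5 subjects.

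**4. Removal unrelated to outcome**

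Each subject is removed with probability r and the threshold is recomputed for each remaining n. The table gives the probability of passing when the true rate equals the goal.

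| r | Safety, N=210, true 88% (alpha 5%) | Efficacy, N=178, true 53% (alpha 2.5%) |
|---|---|---|
| 0% | 4.56% | 2.37% |
| 1% | 3.76% | 2.08% |
| 2% | 3.54% | 2.02% |
| 5% | 3.93% | 2.06% |
| 10% | 3.85% | 2.06% |
| 25% | 3.70% | 2.05% |
| 50% | 3.51% | 1.92% |

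Type I error is not inflated at any of these shares.

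**5. Power**

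Section 16.3 allows only for loss to follow-up: "The sample size was increased for 15% attrition over 12 months". Ineligible subjects removed on top of that reduce the evaluable number.

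- Efficacy at a true 65%: 90.0% at 178, 88.6% at 174, 85.9% at 160.
- Safety at a true 95%: 98.1% at 210, 97.1% at 205.

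**6. Removal related to outcome, near the boundary**

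| Test | All treated subjects | After removal | What was removed |
|---|---|---|---|
| Safety, goal 88% | 192/210, p=0.073, fails | 192/209, p=0.048, passes | 1 failure |
| Safety | 192/210, p=0.073, fails | 191/209, p=0.076, fails | 1 success |
| Efficacy, goal 53% | 107/178, p=0.034, fails | 107/176, p=0.023, passes | 2 non-patent |
| Efficacy | 107/178, p=0.034, fails | 106/176, p=0.032, fails | 1 patent, 1 non-patent |
| Efficacy | 108/178, p=0.024, passes | 107/177, p=0.028, fails | 1 patent |

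The change can go either way. By the plan's own account in Section 4.1, undissected lesions have better patency, so removing them could make passing harder.

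**The case against.** The strongest reply is that the plan already points to one coherent reading. Eligibility is settled before the device is advanced (8.4, 10.2.1, 10.3), and 16.2 refers the reader to 10.2.1 through 10.3.1 for details. Its wording can be taken as a sequence: criteria confirmed, then device advanced. The per-protocol rule and 16.4 both fit only the 10.3.1 definition. On this view the sets coincide, and what remains is a drafting slip.

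This is good evidence of what was intended, but it does not settle the matter. The sets coincide only if screening is free of error, and the per-protocol rule itself expects that it will not be.

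The foreseeability argument is also open to challenge, and part of that challenge stands. Dissection is an eligibility criterion judged by operator visual estimate (7.5.2, item 6; 10.2.1), so a later core-lab reading of none is not clearly a breach. The plan does not say either way. The figure of 5 in 210 is therefore an illustration, not a forecast.

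It is also fair that major eligibility deviations already receive results-blind adjudication. What is missing is any statement that such a finding leaves ITT membership unchanged. Finally, the expected effect is small, and the working above bears that out.

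**Conclusion.** The concern holds. The rule for the primary denominator is stated in two incompatible ways, both are cited for each primary analysis, and nothing says which prevails. The conflict is confined to treated subjects found ineligible.

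The size is modest and conditional. If no such subject is treated, there is no effect. With about 5 affected in 210 (an assumed share borrowed from the earlier TOBA study), power falls by between one and two percentage points. The 85.9% efficacy power at 160 would need about 10% of evaluable subjects to be ineligible (18/178), for which the documents give no basis. A pass/fail reversal in the sponsor's favour needs a result just below the threshold and removals that are mainly failures. The efficacy figures assume a 53% goal, that is, 60% of subjects treated with a drug-coated balloon.

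It should be fixed because the repair costs almost nothing and closes off post hoc removal of treated subjects from two single-arm tests. Confidence in the textual conflict is high; the practical effect on either test depends on a number the documents do not give.

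**What to change.** In the ITT paragraph of Section 16.2, delete everything in "once the subject has met all the inclusion and exclusion criteria including angiographic criteria" after its first word, together with the conjunction that follows it. ITT is then every subject in whom the system is advanced through the introducer sheath, in agreement with 10.3.1, 16.4, Section 19 and the per-protocol rule.

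Add one sentence: *Eligibility breaches, whenever found, do not change ITT membership; they are handled only in the PP set, under its existing results-blind adjudication.*

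The cost is one deletion and one added sentence. The sample sizes of 178 and 210, the performance-goal formula and the test methods are unchanged. The one downside is that ineligible treated subjects stay in both primary analyses; the planned per-protocol analysis shows the results without those whose breach is judged major.

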### 16.3. ENROLLMENT SAMPLE SIZE

The maximum sample size required for the primary objectives is 178 subjects meeting the ITT definition for primary efficacy that are evaluable for the primary patency endpoint measured at 12 months. The sample size was increased for 15% attrition over 12 months, resulting in 210 enrolled subjects. See Sample Size Rationale in **Section 16.7** and **Section 16.8** for sample size calculations specific to each primary endpoint.

### 16.4. ADMINISTRATIVE REPORTS

The study will permit the use of either drug-coated or standard balloons in the angioplasty procedure that immediately precedes Tack placement. The performance goal for the primary efficacy objective depends on the proportion of subjects enrolled, i.e. ITT patients who were treated with standard or drug-coated balloons. Once the index procedure is completed for all enrolled subjects, the proportion of subjects treated with standard balloons and drug-coated balloons will be calculated. The proportions are the weights in the formula to calculate the performance goal. The calculation is described in **Section 16.8 Performance Goal**. The performance goal for primary efficacy will be fixed in advance of or prospectively to the primary efficacy analysis. There is no Type I error adjustment for this report given that no hypotheses will be tested.

### 16.5. JUSTIFICATION FOR POOLING

The investigational sites will be tested for differences in the primary safety and efficacy endpoints using Fisher’s Exact test in the ITT sample. For the primary efficacy endpoint, sites will be additionally stratified by standard vs. drug-coated balloons to evaluate pooling. The Fisher’s Exact test will be performed twice, once for subjects treated with drug-coated balloons and once for subjects treated with standard balloons. Investigational sites with fewer than 10 subjects will be combined for this purpose. If there are any investigational site effects (i.e., statistically significant results at two-sided  $p < .10$ ), a random center effect will be included in a logistic regression model to assess the primary objective. If there are no differences, the data from all investigational sites will be pooled for the analyses.

Additionally, the primary safety and efficacy endpoints will be summarized by US and OUS centers in the ITT sample. The study was not powered to demonstrate the primary efficacy and safety endpoints within the subgroups defined by geography and therefore it is not an expectation that the primary safety and efficacy endpoint will be statistically significant within the subgroups determined by geography.

